## **List of abbreviations**

aMED - Mediterranean Diet Adherence Index

aHEI - Healthy Eating Index

BEDCA - Spanish Food Composition Database

EDC - Electronic data collection

FFQ - Semi-quantitative food frequency questionnaire

HADS - Hospital Anxiety and Depression Scale

HSCSP - Hospital de la Santa Creu i de Sant Pau

HUAV - Hospital Universitari Arnau de Vilanova

IPAQ - International Physical Activity Questionnaire

IR SANT PAU – Institut de Recerca Sant Pau

MEDAS - Mediterranean Diet Adherence Screener

MET - Metabolic equivalent task

PIP - Pediatric Inventory for Parents

T1D - Type 1 diabetes mellitus

## 1. RESUME

|                                  |  |
|----------------------------------|--|
| Promoter identification   | Institut de Recerca Sant Pau (IR SANT PAU)
[name],
[name]
[contact]  |
| Study title               | Dietary changes in adults in the family unit in newly diagnosed pediatric cases of type 1 diabetes: impact of educational actions on routine practice  |
| Code                      | IIBSP-DDM-2023-166   |
| Protocol version and date | Version: 2.0 Approval date: 19/02/2024   |
| Coordinator investigator  | [name], Endocrinology and Nutrition service
Hospital de la Santa Creu i Sant Pau
[name]
[name]
[contact]
e-mail: [contact]  |
| Principal investigator    | [name], IR SANT PAU
e-mail: [contact]   |
| Collaborator researchers  | [name]
[name]
[name]
[name]
[name]
[name]
[name]
[name]
[name]
[name]
[name]
[name]
[name]
[name]           |
| Centros participantes     | Hospital de la Santa Creu i Sant Pau, Barcelona
Hospital Universitari Arnau de Vilanova, Lleida
Hospital Sant Joan de Déu, Esplugues de Llobregat  |
| Reference ethics comitee  | CEI Sant Pau   |
| Principal Aim             | To characterize dietary patterns in the family (parents or guardians) of people newly diagnosed with type 1 diabetes mellitus at the time of diagnosis, and to evaluate their evolution and the effect on health indicators after one year of evolution. |
| Design                    | Observational study on a prospective cohort  |

|  |  |
|--|--|
| Disease of study                              | Type 1 Diabetes mellitus   |
| Methods                                       | Recruitment of 26 family units of newly diagnosed patients with T1D (pre-screened upon hospital admission).
Inclusion visit (within the first week of diagnosis).
Follow-up visits at 6 months.
Final visit at 12 months. |
| Study population and total number of subjects | 26 family units (parents or guardians) of newly diagnosed T1D patients.  |
| Timeline. Study expected duration.            | The expected duration will be 3 years, including a 2-year recruitment period, and a one-year study period:
- Recruitment start: April 2024.
- Recruitment end: April 2026.
- Study end: April 2027.                       |
| Key words                                     | T1D, feeding patterns, family setting, diet, pediatric   |

## 2. ABSTRACT

Type 1 diabetes (T1D) is a chronic disease that often manifests at a young age and requires exogenous insulin administration to ensure adequate glycemic control, in addition to dietary education focused on carbohydrate intake control and healthy eating habits. Diabetic education is carried out in the close family (parents or guardians), whose involvement is necessary to ensure optimal glycemic control and the successful adaptation to a healthy dietary pattern in children and young adolescents. In this sense, parents (or guardians) of children and young adolescents with T1D receive diabetic education too to guarantee the successful adaptation to a healthy dietary pattern. Nevertheless, the modifications in dietary habits within the family unit remain relatively unexplored.

We hypothesize that implementing healthier dietary patterns in the management of newly diagnosed T1D in children and young adolescents has a significant impact on the eating habits of the entire family environment. Therefore, in this study, we aimed at characterizing the dietary patterns of parents or guardians of individuals with newly diagnosed T1D at the time of diabetes diagnosis and at follow-up to assess the impact of routine diet and nutrition education within the family unit, regardless of the changes occurring in the index case itself.

We expect to identify significant changes in the eating habits of the entire family in the first year after the diagnosis of T1D of a family member. These changes, derived from the diabetic education received, offer a potential intervention opportunity for a dietary improvement for the whole family.

**Keywords:** Type 1 diabetes, alimentary patterns, family, diet

### 3. BACKGROUND

Type 1 diabetes mellitus (T1D) is a chronic disease characterized by the autoimmune destruction of pancreatic beta cells, resulting in severely impaired insulin production. Unlike type 2 diabetes, in which insulin resistance plays a predominant role, T1D frequently presents at an early age, requiring exogenous insulin administration to achieve adequate glycemic control (1,2). In addition to insulin administration, choosing an appropriate diet, including carbohydrate counting and establishing good eating habits, is an important pillar in the management of T1D. The goal of dietary change is to ensure the child's proper development, help maintain blood glucose levels within optimal ranges, prevent the development of acute and chronic complications, and improve the quality of life with T1D (1–3). General recommendations for patients with diabetes are similar to those for the general population, based on a balanced diet with a caloric distribution within the range of 50-55% slow-absorbing carbohydrates, 30-35% fats, and 10-15% proteins, limiting the consumption of snacks between meals (2,3). However, the relationship between dietary habits and T1D is inherently complex and multifaceted. Different dietary patterns can influence food absorption and insulin utilization, as well as the postprandial glycemic response (4). Advances in research have led to a better understanding of how food selection and macronutrient distribution are essential for their relationship with glycemic control and insulin requirements in people with T1D (4). In a systematic review we recently published to analyze the effectiveness of medical-nutritional therapy in adolescents with T1D, we observed that dietary interventions delivered to children and adolescents and their families using carbohydrate counting, the use of multimedia applications, and diets rich in vegetables and/or vegetarians have a positive impact on glycemic control and lipid profile of adolescents with T1D (5). However, studies analyzing the effectiveness of medical-nutritional therapy in adolescents with T1D are scarce and of low reliability due to a large number of biases and limitations. On the other hand, we have explored the dietary patterns of adults with T1D in our population, observing that they exhibit healthier eating habits and greater adherence to the Mediterranean Diet than people without diabetes (6).

Due to the individualized nature of diabetes management and the interindividual variability in glycemic response, there is no single dietary strategy that suits all individuals with T1D (3, 7, 8). In fact, implementing new eating habits requires a high degree of self-care on the part of the patient (9). In people with T1D, since they are usually diagnosed in childhood, an additional effort is required by the family unit, which ideally also receives the impact of behavioral interventions to make the necessary dietary changes (10). Thus, with a new diagnosis of a chronic disease such as T1D, not only the individual is exposed to a lifestyle change, but also their family environment. In this regard, it has been documented that parents are willing to make an effort to dedicate more time, as well as increase family financial spending, and adopt organizational changes aimed at maintaining a carbohydrate-controlled diet to maintain adequate blood glucose levels (11). However, these types of changes pose sources of emotional stress, especially related to the patient's glycemic control (12, 13). Additionally, the stress experienced by parents of a child with T1D can negatively impact the patient's glycemic control (13). In very young patients (under 6 years of age), behavioral problems related to eating have been described, which increase the stress perceived by families and are associated with lower adherence to dietary recommendations and worse glycemic control (12).

Diet in a family is shaped by multiple internal and external factors. Therefore, a child's food choices are strongly influenced by those of parents and siblings (14). Thus, parents' dietary patterns shape the home food environment, influence the way the child thinks about food, and consequently influence the children's eating behavior (15, 16). Even the presence of other siblings influences dietary habits, as it has been reported that only children tend to have less healthy dietary patterns compared to families with a larger number of children (17). A recent diagnosis of T1D is one of the external factors that influence the family unit's dietary habits. However, there are very few scientific studies that evaluate the dietary patterns of families with children or adolescents with T1D. Most families with a child with T1D report that the affected child eats the same foods as non-diabetic family members (14). Furthermore, some dietary modifications have been reported based on the dietary guidelines at the time of diagnosis, such as relatives of children with T1D changing their choice of fats

and milk (18). A randomized controlled trial of a behavioral nutrition intervention conducted in families of young people with T1D showed that the dietary pattern measured in terms of diet quality was similar to that observed in the general population (19). However, these studies never evaluate the impact beyond the change in the patient themselves, and not in the family members. To the best of our knowledge, there are no scientific studies evaluating the impact of medical-nutritional therapy on the eating habits and lifestyle of other family members of children and adolescents newly diagnosed with T1D.

## 4. HYPOTHESIS, PRIMARY AND SECONDARY OBJECTIVE

### 4.1 Hypothesis

Given the importance of the family environment in the evolution and management of T1D in children, and that the environment and the patient exert a bidirectional influence, there are no studies focused on studying the impact of diagnosis and management measures on potential changes in the diet and food choices of family members of children/adolescents with T1D. Studies focusing on dietary changes in patients provide insights into dietary recommendations for individuals with T1D, highlighting the importance of individualization and nutritional education in disease management. In this context, we firmly believe that adequately characterizing dietary patterns in adults in families with children with T1D is a very important aspect that has never been previously addressed.

Our initial hypothesis is that the implementation of medical-nutritional therapy in terms of healthy eating for newly diagnosed individuals with T1D has a significant impact on the eating habits and lifestyle of the family members living with the patient.

Furthermore, scientific studies focus solely on analyzing the impact of diabetes education on individuals with T1D themselves, without considering the changes that may occur within the family unit. To our knowledge, no studies have analyzed dietary and lifestyle changes among family members of patients living in the same household as a child/adolescent with newly diagnosed T1D, either in Spain or in other countries. In this regard, there is a lack of studies describing changes in the family unit's diet within routine clinical practice.

### 4.2 Primary objective:

- To evaluate changes in dietary patterns and lifestyle among adults living in the family unit of a newly diagnosed patient with T1D one year after the diabetes diagnosis.

### 4.3 Secondary objectives:

\*Due to the timeliness of the study, we also proposed:

- To characterize changes in the dietary patterns of parents or guardians of patients with T1D during follow-up (6 months after diagnosis).
- To determine, using a questionnaire, changes in the physical activity of the adult subjects in the study at 6 and 12 months.
- To determine, using a questionnaire, the emotional stress produced by the diagnosis and treatment of T1D in the adult parents or guardians belonging to the families of the incident case at 6 and 12 months.
- To determine, using a questionnaire, the level of anxiety and depression produced by the diagnosis and treatment of T1D in the adults in the families at 6 and 12 months.

## 5. METHODS

### 5.1 Study Design

This study will be a prospective, multicenter, observational study. The study will be conducted within the Pediatrics Department of the Hospital de la Santa Creu i de Sant Pau (HSCSP) (Barcelona) and the Hospital Universitari Arnau de Vilanova (HUAV) (Lleida). This study will be launched at the participating centers once a favorable opinion has been obtained from the Research Ethics Committee, and in accordance with the legislative requirements for this type of observational study.

The study design includes an initial visit that will coincide with the patient's inclusion in the study. Prior to the inclusion visit, a pre-screening period is planned. During this period, the potential candidate and their family will be invited, all study procedures will be explained and clarified, the selection criteria will be verified, and the inclusion visit will be scheduled. A follow-up visit will be conducted at 6 months throughout the study. A final visit will be conducted 12 months after enrollment (with a 1-month window).

Adult subjects from 26 households of patients recently diagnosed with T1D are planned to be included.

### 5.2 Study Period

The study period is three years, from April 2024 to April 2027.

#### 5.2.1 Recruitment Period

Participants will be recruited for two years, from April 2024 to April 2026.

#### 5.2.2 Observational Study Period

Participation is for one year from enrollment.

### 5.3 Participant Follow-up

Given this is an observational study, no interventions will be performed on the study participants. Only three visits are required—baseline, 6-month follow-up, and 12-month follow-up—to collect variables and complete the questionnaires. These visits will be conducted as closely as possible to the routine hospital check-ups of the patient with T1D.

### 5.4 Study Population

The study population is the immediate family (parents or guardians) who regularly live with the person newly diagnosed with T1D. The questionnaire will be prioritized for the family member responsible for most of the food in the home. In the case of minors living in two separate family units, the unit in which they spend more than 60% of their time will be included, or both if the estimated time spent living together is equal.

### 5.5 Selection Criteria

#### 5.5.1 Inclusion Criteria:

- Adults.
- Subjects of both sexes.
- Relatives of the pediatric population with newly diagnosed T1D according to ADA criteria.
- Within a maximum of one week of diagnosis of the disease in the index case with T1D in the family.
- Living with the family member with T1D for more than 40% of their time.

- Being responsible for providing food for the household.

#### *5.5.2 Exclusion Criteria:*

- Relatives of patients diagnosed with other types of diabetes (type 2, MODY, gestational, or other causes).
- Participant's family environment with a chronic illness or physiological conditions (e.g., pregnancy) that may influence eating habits.
- Significant dietary changes (switching to vegan, ketogenic, macrobiotic, intermittent fasting diets, etc.) recent to the onset of T1D (within the last month or at the time of inclusion).

#### *5.5.3 Withdrawal criteria:*

All participants have the right to withdraw from the study at any time, withdrawing their consent, without having to justify this decision and without any detriment to their clinical follow-up. Participants may also revoke the use of their data in the analysis, without justifying their decision, and without incurring any liability or harm.

### **5.6 Study procedures**

This study will be launched at the participating centers once a favorable opinion has been obtained from the Research Ethics Committee and in accordance with the legislative requirements for this type of observational studies.

#### *5.6.1 Pre-screening*

Each study subject will be identified by the local investigator at each center during the admission of the newly diagnosed patient. Family members (parents or guardians) of all newly diagnosed subjects with a clinical diagnosis of T1D will be invited to participate. Study procedures will be performed by the local investigators at each participating center, who in some cases will be the same pediatric physicians and nurses as the participants' family members with T1D. A dedicated visit will be scheduled with the local investigator at each center to perform all study procedures in a single visit.

#### *5.6.2 Inclusion*

Each participant invited to participate will be informed about the study both verbally and in writing, using language adapted to their understanding. Participants will be provided with a document called the "Patient Information Sheet" containing all the information of the study, adapted to a simple comprehensive level. No participant will be included until they have been duly informed by the researcher and have freely given their informed consent to participate in the study. Once compliance with all selection criteria has been confirmed and informed consent has been given, data collection will begin by completing an electronic data collection form (EDC), which will record the information available in the patient's medical history or obtained during the inclusion visit.

The inclusion visit will take place within the first week after a family member's T1D diagnosis. This will prevent any lifestyle and dietary changes from being made to the family environment.

The initial clinical evaluation of all included subjects will be performed during the study inclusion visit. Clinical and sociodemographic variables related to the participant (will be collected using an ad-hoc questionnaire and a physical examination. The variables to be collected are defined in **Table 1**. Diet and intake patterns will be collected using questionnaires related to lifestyle and dietary patterns.

These variables will be collected at the inclusion visit, the 6-month follow-up, and at the end of the study at 12 months.

**Table 1.** Study variables

| Variable                            | Source        | Value  |
|-------------------------------------|---------------|--|
| Sociodemographic variables   |               |  |
| Date of birth                       | Questionnaire | dd/mm/yyyy   |
| Age                                 | Questionnaire | Years  |
| Sex                                 | Questionnaire | Male / Female / Other / N/A                                    |
| Gender identity                     | Questionnaire | Male / Female / Other / N/A                                    |
| Area                                | Questionnaire | —  |
| Parents' education level            | Questionnaire | No education / Secondary / Vocational training / University    |
| Family variables             |               |  |
| Number of people in the household   | Questionnaire | Number   |
| Number of children and age          | Questionnaire | Number   |
| Age of child with T1D               | Questionnaire | Number   |
| Person responsible for feeding      | Questionnaire | Mother / Father / Guardian                                     |
| Number of meals per day             | Questionnaire | Number   |
| Number of meals at home per day     | Questionnaire | Number   |
| Type of diet                        | Questionnaire | Omnivorous / Vegetarian / Vegan / Ovo-lacto vegetarian / Other |
| Toxic habits (all)           |               |  |
| Tobacco use                         | Questionnaire | (Smoker, non-smoker, ex-smoker), cigarettes/day                |
| Alcohol use                         | Questionnaire | (User, at-risk user, non-user), SDUs/day                       |
| Drug use                            | Questionnaire | Other, (User, non-user)  |
| Other autoimmune diseases           |               |  |
| Celiac disease                      | Questionnaire | Yes / No   |
| Intolerances / allergies            | Questionnaire | Yes / No. Which  |
| Autoimmune hypothyroidism           | Questionnaire | Yes / No   |
| Others                              | Questionnaire | Yes / No. Which  |
| Other comorbidities                 |               |  |
| Arterial hypertension               | Questionnaire | Yes / No   |
| Dyslipidemia                        | Questionnaire | Yes / No   |
| Diabetes                            | Questionnaire | No / T1D / T2D / LADA / Other                                  |
| Diabetes duration                   | Questionnaire | Years  |
| Cardiovascular disease              | Questionnaire | Yes / No   |
| Liver disease (excluding steatosis) | Questionnaire | Yes / No   |
| Liver steatosis                     | Questionnaire | Yes / No   |
| Renal insufficiency                 | Questionnaire | Yes / No   |
| Clinical variables           |               |  |
| BMI (Body Mass Index)               | Visit         | (kg/m  )   |
| Waist circumference                 | Visit         | (cm)   |
| Diastolic blood pressure            | Visit         | (mm Hg)  |
| Systolic blood pressure             | Visit         | (mm Hg)  |
| Weight                              | Visit         | (kg)   |
| Height                              | Visit         | (cm)   |
| Associated treatments        |               |  |
| Antidiabetic drugs                  | Questionnaire | Yes/No/if yes dosage   |
| Lipid-lowering agents               | Questionnaire | Yes/No/if yes dosage   |
| Antiplatelet agents                 | Questionnaire | Yes/No/if yes dosage   |
| Anticoagulants                      | Questionnaire | Yes/No/if yes dosage   |
| Antihypertensives                   | Questionnaire | Yes/No/if yes dosage   |

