### **11. STUDY RESOURCES**

This project uses the resources and infrastructure of the two participating centers.

At the HSCSP, the Pediatric Endocrinology Unit has three pediatric endocrinology specialists and a nurse specializing in nutrition who is responsible for the diabetes education of patients with T1D. The hospital serves five districts in the city of Barcelona, with a population of over 400,000. It is estimated that the number of new T1D diagnoses is 15 patients per year, to which will be added those diagnosed up to the age of 20. The estimated total is 24 patients. Patients are admitted through the emergency department or referred from other primary care centers and are admitted for one week, at which point the professionals begin nutritional education. The Endocrinology Department at Sant Pau Hospital has a research unit with statistical support available for data evaluation and management, as well as for processing results for analysis.

The Pediatric Endocrinology Unit of the Pediatric Department at HUAV in Lleida has two pediatric specialists with extensive experience in diabetes treatment and a dedicated diabetes educator nurse with specific training in diabetes and nutrition education and years of experience caring for patients. The unit serves a population corresponding to the province of Lleida, as well as patients referred from the Franja de Aragón region. Approximately 15 patients are admitted each year for onset diabetes. Admission care is provided for children up to the age of 15, and newly diagnosed children up to the age of 20 will be added; for an estimated total of 25 patients at this center. Patients receive education upon diagnosis, both from doctors and from nursing professionals, as well as from the diabetes educator. Patients are usually admitted for a week. Subsequently, they are followed up in outpatient clinics by various team professionals. Basic supervision is also provided by the mental health team at the CSMIJ in Lleida. Initial training includes nutritional education, which recommends the ideal number of servings for each patient and their distribution throughout the day, in addition to comprehensive education on healthy dietary habits. It is conducted annually.

Within the teaching function, a course is offered to teaching staff from schools and high schools in the area, in collaboration with the hospital's teaching classroom.

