The Sant Joan de Déu Hospital, a leading pediatric hospital in the Barcelona area, is also participating in the study. Its endocrinology unit receives 13,000 visits per year, with consultations for DM1 being one of the most frequent. They have a team of pediatric endocrinologists and nurses who provide educational interventions to

patients and their families during the stay following a DM1 diagnosis. The hospital has a web portal with information, advice, and other resources for patients with DM1 and their families. The number of new DM1 diagnoses varies widely, but the expected recruitment rate is expected with the participation of both hospitals.

These hospitals have affiliated research institutes, the Lleida Biomedical Research Institute, the IR Sant Pau, and the Sant Joan de Déu Research Institute, which have the infrastructure and personnel necessary to carry out the project. The principal investigator of the project belongs to the Sant Pau Research Institute. The crucial leadership of women in this research not only promotes diversity and equity in scientific research but also represents an essential contribution to elevating excellence in biomedical research, opening new paths and approaches in the field of health. [name] is a dietitian-nutritionist, with a PhD in Biomedicine, with extensive experience in the field of basic and translational research focused on nutrition, endocrinology, and complications associated with diabetes. She is an affiliated researcher with the CIBERDEM research group at the Sant Pau Biomedical Research Institute and is part of the Endocrinology, Diabetes, and Nutrition research group, both led by [name]. This group has extensive experience in the study of diabetes and complications associated with dietary and lifestyle habits, which has resulted in a large number of national and international projects and, consequently, scientific publications in high-impact international journals.

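### Section 5.6.2 claims the one-week window rules out early dietary change, but education falls in that week and nothing places the baseline questionnaires before it

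*Protocol*

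**What the plan says.** Section 5.6.2 schedules inclusion no later than one week after the child's diagnosis and gives the reason: "This will prevent any lifestyle and dietary changes from being made to the family environment". Section 8 (Phase 2) repeats the one-week limit. Section 5.6.1 adds: "A dedicated visit will be scheduled with the local investigator at each center to perform all study procedures in a single visit".

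Section 11 describes routine education at each site:

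- **HUAV:** "Patients receive education upon diagnosis, both from doctors and from nursing professionals, as well as from the diabetes educator". The initial training covers servings and their distribution over the day, "in addition to comprehensive education on healthy dietary habits".
- **Sant Joan de Déu:** the team gives educational interventions to "patients and their families during the stay following a DM1 diagnosis".
- **HSCSP:** patients "are admitted for one week, at which point the professionals begin nutritional education".

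The abstract says that "parents (or guardians) of children and young adolescents with T1D receive diabetic education too".

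Two provisions touch on early change. Section 5.5.2 excludes significant diet switches "recent to the onset of T1D (within the last month or at the time of inclusion"), with vegan, ketogenic, macrobiotic and fasting diets as examples in an open list. Section 5.7.1 provides a first-visit question about changes in dietary habits in the year before the study.

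**The concern.** The study asks what routine education does to the diet of the adults in the household. Its baseline should therefore come before education, and closeness to diagnosis does not secure that. A visit window limits the time that has passed; it does not stop anyone from changing what they eat or how they describe it.

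The analysis compares each adult with their own baseline (Sections 6.3 and 6.4), and there is no control group. If teaching has already improved the diet, or the answers about it, when the baseline forms are completed, that part of the change is subtracted from the estimate. If the order of teaching and questionnaires is not recorded, the analysis has no planned means of seeing whether this happened.

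**Working it through.** This is mainly a comparison of passages, with one small calculation.

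**Step 1. Does education fall inside the baseline window?** The window runs from day 0 to day 7 after diagnosis.

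| Site | Timing of education (Section 11) | Inside the window? |
|---|---|---|
| HUAV | At diagnosis | Yes |
| Sant Joan de Déu | During the stay after diagnosis, families included | Yes, for any teaching in the first seven days |
| HSCSP | Tied to the one-week admission | Unclear: the wording can mean its start or its end |

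The HUAV text speaks of patients; the abstract extends education to parents. Two sites are enough to contradict an absolute claim.

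**Step 2. Does any section set the order?** Sections 5.1, 5.5.1, 5.6.1, 5.6.2, 6.2 (Table 2) and 8 time the baseline against diagnosis or enrolment only. Section 5.6.1 groups the procedures into one visit but does not place that visit before the first teaching session. A baseline completed after teaching complies fully with the protocol.

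**Step 3. Do the existing safeguards close the gap?**

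- The Section 5.5.2 exclusion reaches marked diet switches. Ordinary uptake of healthy-eating advice is not clearly within it.
- The Section 5.7.1 question, read plainly, would reach a parent who changed diet on days 1 to 4 and enrolled on day 5.
- Neither reaches a parent whose diet is unchanged but who answers differently after being taught.
- Table 1 has no entry for diabetes education received; its only education item is the parents' schooling. Section 6.5 does not list the issue as a limitation.

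**Step 4. Which dietary measures are exposed?**

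- *FFQ:* Section 5.7.1 gives a reference period of one year. For a visit on day 7, the latest allowed, the share of the recall period after diagnosis is 7 / 365 = 0.019, or 1.9%. This counts days of intake. It does not measure altered reporting.
- *aMED and aHEI:* Table 2 lists no separate form for either. If they are scored from the FFQ, the same 1.9% applies.
- *MEDAS:* it is scored on reported consumption, and the protocol states no reference period, so no corresponding share can be calculated.

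**Step 5. Is the sample size affected?** Section 6.4 gives 26 family units for a 1-point aMED difference (paired, 80% power, alpha 5%). The SD of the change is not printed, so 26 cannot be reproduced directly; solved backwards with a two-sided paired t-test, it implies an SD of about 1.75. The present point does not depend on that figure and gives no reason to alter it.

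**The case against.** The strongest reply is that real early change is already partly handled. The exclusion list is open-ended and reaches up to inclusion, and the first-visit question plausibly covers the days between diagnosis and enrolment. The child is usually in hospital that week, so the household menu has little time to change. This stands in part: it narrows the concern to small unreported changes and to changed reporting.

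A second reply is that the MEDAS form is not reproduced. The protocol's silence on a reference period does not show that the instrument lacks one. That is correct, so the claim is only that the protocol states none.

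Four stronger readings are tempting, and the documents support none of them:

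- *Parents' diets have already changed by baseline.* Nothing in the protocol shows this.
- *The MEDAS change will be understated by a calculable amount.* Understatement is the likely direction, but teaching could also make people more self-critical and lower their baseline score. A power-loss figure would need an invented fraction of early change and an SD borrowed from aMED.
- *The FFQ is safe because only 1.9% of its window follows diagnosis.* That figure covers intake; reporting on the FFQ could shift as well.
- *The order of events could never be recovered.* Section 5.6.1 says that some investigators are the treating staff, and Section 5.6.2 lets the EDC draw on the medical history, so site records might hold teaching dates. The protocol simply does not plan to collect them.

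**Conclusion.** The point holds in limited form. The safeguard in Section 5.6.2 does not do what it claims: at two of the three sites education falls in the week in which baseline is taken, and the protocol neither orders the two nor records which came first. The baseline of an uncontrolled pre-post study of education may therefore be partly exposed.

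Some understatement of change is likely, but its size and direction cannot be established from the protocol. MEDAS is the most exposed dietary measure. Actual intake on the FFQ is largely protected (at most 1.9% of the recall year), as are aMED and aHEI on the assumption that they are scored from it. The sample-size figure is untouched.

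The conclusion rests on reading Section 11 as describing what happens in the first week, and on the abstract's statement that parents are taught. This is a cheap improvement worth making; it does not invalidate the design.

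**What to change.** 1. In Section 5.6.2, replace the absolute claim with a statement that the one-week window is meant to limit early lifestyle and dietary change.
2. Add one line to Section 5.6.2: the baseline diet questionnaires are completed before the participant's first diabetes-education session wherever this neither alters routine care nor shortens the time to consider consent.
3. Add to Table 1 and the EDC the date of the baseline questionnaires, the date of any diabetes education already received, and the order when both fall on the same day.
4. Use these fields for a sensitivity check by prior exposure, declared as descriptive given about 26 families.

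The cost is one reworded sentence, one line on order and two or three EDC fields. Questionnaires first will not be feasible for every family, which is why the dates are needed. The MEDAS wording should stay as it is: a special baseline instruction would make that form differ from the 6- and 12-month forms and from the validated version.
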